12.1.5 Significance Level for Inferential Analysis

Unless stated otherwise, all statistical tests will be two-sided and conducted at the 5% level, and all quoted confidence intervals will be two-sided 95% confidence intervals.

The primary endpoints will be tested using a multiple testing procedure to preserve the overall alpha level by simultaneously testing the endpoints using a closed procedure with each test performed at an one-sided alpha level of 2.5%. This implies that statistical significance is required for all primary endpoints in order to be able to make confirmatory claims about any of the endpoints.

Further details will be provided in the SAP.

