Table 21 describes the expected coefficients of variation (CV) and mean ratios (MR) between THS 2.2 Menthol and the mCC control arm in COHb, 3-HPMA, MHBMA and S-PMA based on data from a single-center, open-label, randomized, controlled, 2-arm parallel group study to evaluate the exposure to selected smoke constituents in smoking, apparently healthy subjects switching from conventional cigarettes to THS 2.1 compared to subjects continuing to smoke CC for 5 days, the ZRHX-EX-01 study (ClinicalTrials.gov: ID: NCT01780714) sponsored by PMI. The mean ratios and coefficients of variations for THS 2.1/CC are expected to be the same as THS 2.2 Menthol/mCC.

Table 21. Expected Mean Ratios and coefficients of Variation for THS 2.2 Menthol/mCC

THS 2.2 Menthol /mCC	
	MR (CV)
COHb	0.44 (0.14)
3-HPMA	0.28 (0.20)
MHBMA	0.11 (0.47)
S-PMA	0.07 (0.50)

Abbreviations: 3-HPMA = 3-hydroxypropylmercapturic acid; mCC = menthol conventional cigarettes; COHb = carboxyhemoglobin; CV = coefficient of variation; MHBMA = monohydroxybutenyl mercapturic acid; MR = mean ratio; S-PMA = S-phenylmercapturic acid; THS 2.2 = Tobacco Heating System 2.2.

Based on these two sets of assumptions on the mean ratios and coefficients of variations for the four primary BoExp on Day 5, the power to demonstrate a reduction was computed.

The comparison will be run on the per protocol population as defined in Section 12.4.2.

Subjects are expected not to have any reason for exclusion from the per protocol population in the confinement period for THS 2.2 Menthol arm and in ambulatory and confinement condition for the mCC arm.

50% of the subjects are expected to be excluded from the per protocol population in the THS 2.2 Menthol arm in the ambulatory (mostly due to lack of compliance to the randomized product). Thus the expected populations on which the reductions will be assessed as described in Table 22.

Table 22. Sample Size to Assess the Reductions

Sample size to assess the reduction (THS 2.2 Menthol:/mCC)	
COHb	80:40
3-HPMA	80:40
MHBMA	80:40
S-PMA	80:40
Total NNAL	40:40

Abbreviations: 3-HPMA = 3-hydroxypropylmercapturic acid; Total NNAL = total 4-(methylnitrosamino)-1-(3-pyridyl)-1-butanol mCC = menthol conventional cigarettes; COHb = carboxyhemoglobin; MHBMA = monohydroxybutenyl mercapturic acid; S-PMA = S-phenylmercapturic acid; THS 2.2 = Tobacco Heating System 2.2.

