Data and information contained in this document are considered to constitute trade secrets and confidential commercial information, and the legal protections provided to such trade secrets and confidential information are hereby claimed under the provisions of United States law. No part of this document may be publicly disclosed without the written consent of Philip Morris International.

Table 23 describes the expected power to demonstrate a reduction on 5 primary BoExp in smokers switching from CC to THS 2.2 Menthol as compared to those continuing to smoke mCC, using one-sided test with 2.5% type I error probability using the assumptions from YVD-CS01-EU and ZRHX-EX-01 given a sample size of 160 smokers (~80 in THS 2.2, ~40 in CC, and ~40 in the SA arm). Therefore subjects will be enrolled into the study until there are 160 smokers in the FAS population.

Table 23. Expected power (YVD-CS01-EU and ZRHX-EX-01 studies assumptions)

Assumptions	Reduction					
	50%	51%	52%	53%	54%	55%
YVD-CS01-EU	94%	88%	81%	70%	56%	38%
ZRHX-EX-01	98%	97%	92%	76%	41%	6%

Power considerations related to secondary endpoints of biological changes:

The sample size is sufficient to obtain 95% CIs for the ratio between (geometrical) mean levels of primary BoExp in THS 2.2 Menthol and SA with upper and lower limits deviating not more than 18% from the point estimates, with an 80% overall probability of achieving the desired precision of estimating the true mean.

This study has 80% power using a one-sided test with 2.5% type I error probability:

- To detect a 0.631 [mL/min/kg] (29%) difference between THS 2.2 Menthol and mCC in CYP1A2 activity, as measured by the caffeine clearance, assuming a SD of 0.564. Effect size and variability are derived from data obtained in the YVD-CS01-EU study sponsored by PMI.
- To detect a 24.71 [ng/g creatinine] (20%) difference between THS 2.2 Menthol and mCC in 11-DTX-B2, assuming a SD of 43.78, as reported by Saareks et al., 2001. The anticipated effect size of THS 2.2 Menthol is assumed to be about 90% of the effect of smoking cessation reported in the paper by Saareks et al., 2001.

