12.5 Primary Analysis

12.5.1 Primary Endpoint Analysis Variables

The primary endpoints are:

- COHb on Day 5
- MHBMA on Day 5
- 3-HPMA on Day 5
- S-PMA on Day 5
- Total NNAL on Day 90.

See Section 3.4.1.

Evaluation criterion:

The study will be considered successful, if the study demonstrates a 50% reduction or more for all five primary BoExp in the THS 2.2 Menthol arm compared to the mCC arm, using a one-sided test with 2.5% type I error probability.

Data and information contained in this document are considered to constitute trade secrets and confidential commercial information, and the legal protections provided to such trade secrets and confidential information are hereby claimed under the provisions of United States law. No part of this document may be publicly disclosed without the written consent of Philip Morris International.

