12.5.4 Confirmatory Analysis

The hypothesis to be tested is that the geometric mean level of the BoExp for THS 2.2 Menthol is lower relative to mCC.

For primary BoExp, the hypothesis will be tested on Day 5 for monohydroxylbutenyl-mercapturic acid (MHBMA), 3-hydroxypropylmercapturic acid (3-HPMA), S-phenylmercapturic acid (S-PMA), and carboxyhemoglobin (COHb), and on Day 90 Visit for Total NNAL.

The transformed BoExp data on a natural log scale will be analyzed by means of a generalized linear model using product arm as covariate adjusting for the following baseline information: sex, average cigarette consumption over the previous 4 weeks, and baseline value of endpoint. The test will be declared significant if the contrast THS 2.2 Menthol vs mCC is significant. Estimates of differences between groups will be back-transformed to provide relative effects.

Assumptions of the analysis of variance model will be tested. Markedly non-lognormally distributed BoExp data will be transformed or analyzed by appropriate non-parametric methods.

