**Table 20: Expected Power (YVD-CS01-EU and ZRHX-EX-01 Studies Assumptions)**

Assumptions	Reduction					
	50%	51%	52%	53%	54%	55%
YVD-CS01-EU	94%	88%	81%	70%	56%	38%
ZRHX-EX-01	98%	97%	92%	76%	41%	6%

A total of 160 smokers (80 in THS 2.2 menthol, 40 in mCC, and 40 in the SA arm) will be randomized to demonstrate a reduction of at least 50% on 5 primary BoExp in smokers switching from mCC to THS 2.2 Menthol as compared to those continuing to smoke mCC, using one-sided test with 2.5% type I error probability.

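### The ZRHX-EX-01 powers stated for 52%, 53% and 54% reductions exceed the power of COHb alone, so they do not follow from the printed inputs

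*Protocol*

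**What the plan says.** Protocol section 12.2 presents Table 23, headed "Table 23. Expected power (YVD-CS01-EU and ZRHX-EX-01 studies assumptions"), as "the expected power to demonstrate a reduction on 5 primary BoExp", "using one-sided test with 2.5% type I error probability". SAP section 8 repeats it as "Table 20: Expected Power (YVD-CS01-EU and ZRHX-EX-01 Studies Assumptions"). For demonstrated reductions of 50/51/52/53/54/55% both tables state:

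- YVD-CS01-EU: 94/88/81/70/56/38%
- ZRHX-EX-01: 98/97/92/76/41/6%

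The ZRHX-EX-01 inputs are in protocol Table 21 ("Table 21. Expected Mean Ratios and coefficients of Variation for THS 2.2 Menthol/mCC") and SAP Table 18. The YVD-CS01-EU inputs are in protocol Table 19 and SAP Table 16. The Total NNAL input is in protocol Table 20 and SAP Table 17, and the numbers per arm are in protocol Table 22 and SAP Table 19.

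Protocol section 12.5.1 counts the study as a success "if the study demonstrates a 50% reduction or more for all five primary BoExp". Section 12.1.5 says of the testing procedure: "This implies that statistical significance is required for all primary endpoints". Neither document says how the five powers were combined or what correlation was assumed.

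**The concern.** When every endpoint must succeed, the chance that all do is at most the chance that the weakest one does. This holds under any dependence between endpoints, so it tests the table without knowing how the sponsor combined the powers. In the ZRHX-EX-01 set, COHb has the ratio closest to the margin (0.44 against 0.50 down to 0.45) and is the weakest endpoint from 52% onward. If the joint figure is above the COHb power, the table and its inputs disagree.

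At stake is one of the plan's two scenarios for how far beyond 50% a reduction could be shown. It is the scenario built on THS 2.1, which protocol section 2.1.2 calls the predecessor of THS 2.2. The mismatch was carried unchanged from the protocol into the SAP.

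**Working it through.** **Method.** The analysis is on the natural log scale (protocol section 12.5.4: "The transformed BoExp data on a natural log scale will be analyzed by means of a generalized linear model"). For each endpoint:

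- sd = √ln(1 + CV²)
- δ = ln(1 − reduction) − ln(mean ratio)
- SE = sd × √(1/n₁ + 1/n₂)
- power from the noncentral t distribution with noncentrality δ/SE and n₁ + n₂ − 2 df, one-sided 2.5%

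**Inputs, mean ratio (CV).**

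| Endpoint | YVD-CS01-EU | ZRHX-EX-01 | n (THS:mCC) |
|---|---|---|---|
| COHb | 0.40 (0.32) | 0.44 (0.14) | 80:40 |
| 3-HPMA | 0.30 (0.50) | 0.28 (0.20) | 80:40 |
| MHBMA | 0.15 (0.70) | 0.11 (0.47) | 80:40 |
| S-PMA | 0.20 (0.70) | 0.07 (0.50) | 80:40 |
| Total NNAL | 0.30 (0.60) | 0.30 (0.60) | 40:40 |

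**Step 1: reproduce the YVD-CS01-EU row.** The Bonferroni lower bound on joint power is 1 − Σ(1 − powerᵢ). At 55%, COHb has 48.89% power, 3-HPMA 99.26% and Total NNAL 89.79%; the other two round to 100%. The bound is 100 − 51.11 − 0.74 − 10.21 = 37.94%, against 38% stated.

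| YVD-CS01-EU | 50% | 51% | 52% | 53% | 54% | 55% |
|---|---|---|---|---|---|---|
| Stated | 94 | 88 | 81 | 70 | 56 | 38 |
| Bound | 93.8 | 88.8 | 81.1 | 69.9 | 55.2 | 37.9 |
| Product (independence) | 93.9 | 89.1 | 81.6 | 71.2 | 58.1 | 43.6 |

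The bound matches all six cells within 1 point. The product misses at 54% and 55%.

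**Step 2: COHb alone under ZRHX-EX-01.** sd = √ln(1.0196) = 0.1393, and SE = 0.1393 × √(1/80 + 1/40) = 0.0270, with 118 df.

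| Reduction | δ | δ/SE | COHb power | Stated joint power | Excess |
|---|---|---|---|---|---|
| 52% | ln(0.48/0.44) = 0.0870 | 3.23 | 89.2% | 92% | 2.8 |
| 53% | ln(0.47/0.44) = 0.0660 | 2.44 | 67.9% | 76% | 8.1 |
| 54% | ln(0.46/0.44) = 0.0445 | 1.65 | 37.2% | 41% | 3.8 |

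A normal approximation gives 89.7%, 68.6% and 37.7%, still below the stated values.

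**Step 3: the whole ZRHX-EX-01 row.** 3-HPMA, MHBMA and S-PMA round to 100% throughout, so only COHb and Total NNAL matter.

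| ZRHX-EX-01 | 50% | 51% | 52% | 53% | 54% | 55% |
|---|---|---|---|---|---|---|
| Stated | 98 | 97 | 92 | 76 | 41 | 6 |
| Weakest endpoint (cap) | 98.2 | 97.4 | 89.2 | 67.9 | 37.2 | 12.8 |
| Product | 98.0 | 95.2 | 85.9 | 64.3 | 34.5 | 11.5 |
| Bound | 97.9 | 95.1 | 85.5 | 62.6 | 29.8 | 2.6 |
| Bound, COHb CV 0.12 | 98.2 | 97.0 | 92.4 | 75.4 | 40.3 | 5.7 |

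The 50% cell reproduces and the 51% cell is within 2 points. The cells at 52%, 53% and 54% break the cap. The last line matches every stated cell within 1 point.

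**Step 4: rounding of the inputs.** COHb and Total NNAL ratios and CVs were varied within their two-decimal rounding. The best fit with the bound (COHb 0.4365, CV 0.136; Total NNAL 0.305, CV 0.595) still misses one cell by about 2.7 points. The best fit with the product misses one by about 7 points.

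**The case against.** The strongest reply is that the cap depends on a ratio printed to two decimals. An unrounded COHb ratio of 0.437, which prints as 0.44, with CV 0.14 gives COHb alone 93.2%, 76.3% and 47.0% at 52%, 53% and 54%, and no stated cell then exceeds it. That stands. The three figures are impossible for the inputs as printed, but not for every input that rounds to them. It does not rescue the row, because no choice tried within rounding reproduces all six cells.

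A second reply is that nothing turns on these columns. Success and the 80% power claim are both set at 50%, and no decision rule uses 51% to 55%. That also stands and limits the weight of the point.

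A reader might go further and infer that both rows are wrong and should be replaced by products over independent endpoints. The documents do not support this. They state no independence assumption, and the YVD-CS01-EU row fits the more conservative bound. Replacing it would raise its 55% cell from 38% to 44%. The 6% in the ZRHX-EX-01 row at 55% is likewise not shown to be wrong, since it lies between the bound (2.6%) and the cap (12.8%). Gaps of 6 to 12 points at 52% to 54% appear only when the row is measured against the independence product.

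**Conclusion.** The ZRHX-EX-01 powers at 52%, 53% and 54% do not follow from the printed inputs. They are too high by at least 2.8, 8.1 and 3.8 points, whatever the correlation between endpoints. This rests on the printed COHb ratio and CV, 80:40 subjects, log-scale analysis and one-sided 2.5% tests.

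One method, the Bonferroni bound, fits both rows within 1 point if the COHb CV behind the ZRHX-EX-01 row was about 0.12 instead of 0.14. That suggests an input mismatch between Tables 21 and 23, but it is an inference. The documents do not show which table is in error.

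Nor should the point be read as a sign that the trial is underpowered. Both 50% cells (94% and 98%) reproduce, so the sample size and the claim of 80% power at the success criterion stand.

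**What to change.** Check the COHb mean ratio and CV against the ZRHX-EX-01 study data. Then do one of the following:

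- If the printed inputs are wrong or too coarsely rounded, correct them or print them to more decimals in protocol Table 21 and SAP Table 18, and confirm that the power row follows.
- If the printed inputs are right, restate the ZRHX-EX-01 row of protocol Table 23 and SAP Table 20. With the bound that fits the other row it becomes 98/95/86/63/30/3%.

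In either case leave the YVD-CS01-EU row as it is, and add one sentence to each document saying how the five powers were combined. The cost is one look-up, a few table cells and one sentence in each document. Design, sample size and analysis do not change.

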- To describe the change in CYP1A2 enzymatic activity in smokers switching from mCC to THS 2.2 Menthol as compared to smokers continuing to smoke mCC and to SA.
 - Molar metabolic ratio of paraxanthine (PX)/caffeine (CAF) in plasma on Day 5 and Day 90 Visit.

- To determine the changes in lung function in smokers switching from mCC to THS 2.2 Menthol as compared to those continuing to smoke mCC.
 - Full lung functions: Diffusion capacity for lung CO (DLCO), rate constant of CO (KCO), forced expiratory volume in 1 second (FEV1), forced vital capacity (FVC), vital capacity (VC) expressed as L, total lung capacity (TLC), forced residual volume (FRV), inspiratory capacity (IC), mid expiratory flow (25-75).
- To monitor the safety profiles during the study.
 - AEs/ SAEs, and device events including THS 2.2 Menthol malfunction/misuse.
 - Respiratory symptoms: cough assessment by visual analogue scale (VAS) and Likert scales and one open question.
 - Vital signs.
 - Electrocardiogram (ECG).
 - Clinical chemistry, hematology, and urine analysis safety panel.
 - Physical examination.
 - Concomitant medications.
- To monitor selected risk markers in a confinement and ambulatory setting in smokers switching from mCC to THS 2.2 Menthol as compared to smokers continuing to smoke mCC and to SA.
 - Systolic and diastolic blood pressure on Day 6, Day 30 Visit, Day 60 Visit, and Day 90 Visit.
 - High sensitive C-reactive protein (hs-CRP), homocysteine, blood glucose, low density lipoprotein (LDL), high density lipoprotein (HDL), triglycerides (TG), total cholesterol (TC) in serum on Day 30 Visit, Day 60 Visit, and Day 90 Visit
 - Fibrinogen in plasma on Day 30 Visit, Day 60 Visit, and Day 90 Visit
 - Hemoglobin A1c in blood on Day 90 Visit.
 - Apolipoprotein A1 (Apo A1) and Apolipoprotein B (Apo B) in serum on Day 90 Visit.
 - Soluble inter-cellular adhesion molecule-1 (sICAM-1) in serum on Day 6, on Day 30 Visit, Day 60 Visit and Day 90 Visit.
 - White blood cell (WBC) and platelet count in blood on Day 6, Day 30 Visit, Day 60 Visit, and Day 90 Visit.
 - 8-epi-prostaglandin F2 α (8-epi-PGF2 α) and 11-dehydro-thromboxane B2 (11-DTX-B2) in 24-hour urine on Day 5 and on Day 30 Visit, Day 60 Visit, and Day 90 Visit (expressed as concentration adjusted for creatinine).

- Body weight and waist circumference on Day 90 Visit.

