7.5.2.2 CYP1A2 activity test

CYP1A2 activity will be assessed in plasma by measuring PX and CAF concentrations and calculating the PX/CAF molar metabolic ratio (Faber et al., 2004) on Day 0, Day 5, and Day 90 Visit (Day 90). Samples to measure PX and CAF will be drawn approximately 6 hours (± 15 minutes) after the intake of one “vivarin” caffeine tablet (around 200 mg caffeine) with 240 mL ± 10 mL water (Faber et al., 2004).

The exact time of intake of the caffeine tablet in the morning and of the time of blood sampling 6 hours [± 15 minutes] later must be recorded.

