### 7.1.3 CYP1A2

CYP1A2 activity is calculated as the molar metabolic ratio of PX / CAF in plasma, both expressed in molar equivalent (nmol/L).

The conversion factor will be applied as follows:

PX

The molecular weight is 180.166 g/mol (**Chemical Information Specialized Information Services RN:611-59-6**). Therefore to convert PX in ng/mL to nmol/L the result in ng/mL is multiplied by 5.550.

CAF

The molecular weight is 194.193 g/mol. (**Chemical Information Specialized Information Services RN:58-08-2**). Therefore to convert CAF in ng/mL to nmol/L the result in ng/mL is multiplied by 5.150.

The converted results will be calculated to three decimal places and the ratio will be reported as a percentage with two decimal places.

If either of the PX or CAF concentration is LLOQ then the ratio will not be calculated.

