#### 12.6.2.4 CYP1A2 Activity

CYP1A2 activity will be measured in plasma on Day 0, Day 5 and Day 90. In this study the CYP1A2 activity will be calculated using the molar ratio of PX and CAF, as described in Section 7.1.3 “CYP1A2”. Descriptive statistics of the values and percent change on Days 5 and 90 from Day 0 and supportive listings will be provided.

The analysis will compare the log-transformed Day 5 values between the THS 2.2 Menthol and mCC arms and between the THS 2.2 Menthol and SA arms. ANCOVA models will be used on CYP1A2 activity levels with terms for log-transformed baseline, sex, average daily mCC consumption over the last 4 weeks as reported during screening and randomization arm. No adjustment will be made for multiple comparisons. If the results from the Day 5 analysis are significant (one-sided p-value <0.025) then the statistical significance will be repeated for the analysis at the Day 90 values. The SAS code will be similar to that described in Section 12.6.1.3 “Sensitivity Analysis”.

Geometric LS means for each product along with the ratio (THS 2.2 Menthol :mCC) and 95% CI will be presented in the tables.

CYP1A2 activity will also be examined to compare the observed reductions in THS 2.2 Menthol vs. SA using the same methodology as above.

If there are any CYP1A2 assessments performed within 5 half-lives since the use of a concomitant medication affecting CYP1A2 activity, the analysis will be repeated by excluding these assessments for both the PP Set and FAS

All summaries and analyses will be performed on the FAS and PP Set.

The data will be presented in the below outputs:

TFL number	Title
TABLES	
15.2.4.23.1	Descriptive Statistics of CYP1A2 Activity (%) – PP Set
15.2.4.23.1.1	Descriptive Statistics of CYP1A2 Activity (%) Excluding Assessments within 5 Half-Lives of a Concomitant Medication Affecting CYP1A2 Activity – PP Set
15.2.4.23.2	Descriptive Statistics of CYP1A2 Activity (%) – FAS
15.2.4.23.2.1	Descriptive Statistics of CYP1A2 Activity (%) Excluding Assessments within 5 Half-Lives of a Concomitant Medication Affecting CYP1A2 Activity – FAS
15.2.4.24.1	Analysis of CYP1A2 Activity (%) – PP Set
15.2.4.24.1.1	Analysis of CYP1A2 Activity (%) Excluding Assessments within 5 Half-Lives of a Concomitant Medication Affecting CYP1A2 Activity – PP Set
15.2.4.24.2	Analysis of CYP1A2 Activity (%) – FAS

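### Protocol 12.2: the CYP1A2 power line's difference, SD, arm sizes and 80% power do not agree, and it powers caffeine clearance instead of the planned PX/CAF ratio

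*Protocol*

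**What the plan says.** Under its power considerations for secondary endpoints, Protocol 12.2 opens with one claim that covers two bullets: "This study has 80% power using a one-sided test with 2.5% type I error probability". The first bullet is the CYP1A2 line: "To detect a 0.631 [mL/min/kg] (29%) difference between THS 2.2 Menthol and mCC in CYP1A2 activity". The same bullet then names the measure and its spread: "as measured by the caffeine clearance, assuming a SD of 0.564". It says that effect size and variability come from the sponsor's earlier study YVD-CS01-EU. The second bullet is for 11-DTX-B2: a difference of 24.71 ng/g creatinine (20%) with SD 43.78. The arm sizes appear a little earlier in the same section: "given a sample size of 160 smokers (~80 in THS 2.2, ~40 in CC, and ~40 in the SA arm".

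The endpoint itself is defined differently. Protocol 3.4.2 lists "Molar metabolic ratio of paraxanthine (PX)/caffeine (CAF) in plasma on Day 5 and Day 90 Visit". Protocol 7.5.2.2 says "CYP1A2 activity will be assessed in plasma by measuring PX and CAF concentrations and calculating the PX/CAF molar metabolic ratio", from a sample drawn about 6 hours after a caffeine tablet. SAP 7.1.3 agrees: "CYP1A2 activity is calculated as the molar metabolic ratio of PX / CAF in plasma". SAP 12.6.2.4 gives the analysis: "The analysis will compare the log-transformed Day 5 values between the THS 2.2 Menthol and mCC arms", by ANCOVA, with the result shown as a ratio of geometric means. SAP section 8 does not carry the CYP1A2 power line forward.

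**The concern.** There are two separate problems. First, an effect of more than one standard deviation, tested with 80 against 40 subjects, should have power close to 100%. A stated 80% therefore suggests that one of the printed figures is wrong. Second, a difference and SD in mL/min/kg describe clearance, and the study plans no clearance endpoint or analysis.

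What is at stake is interpretation. CYP1A2 is a secondary endpoint with formal inference: Day 5 is tested first, and Day 90 significance is assessed only if Day 5 is significant. A reader facing a null or borderline result would want to know what effect the study could detect. The line does not give that reliably for clearance, and does not give it at all for the planned ratio.

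**Working it through.** **Inputs, all from Protocol 12.2.** Difference 0.631, SD 0.564, one-sided alpha 0.025, arms about 80 (THS 2.2 Menthol) and 40 (mCC). Protocol 12.2 expects no per-protocol exclusions in these two arms during confinement, so 80:40 is also the expected Day 5 per-protocol size. The smallest planned per-protocol comparison in Table 22 is 40:40 (Total NNAL).

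**Trying to reproduce the stated 80%.** Standardised difference d = 0.631/0.564 = 1.119.

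- At 80:40: sqrt(1/80 + 1/40) = 0.1936, so the non-centrality is 1.119/0.1936 = 5.78. The normal approximation is Φ(5.78 − 1.96) = 0.99993. The non-central t (118 df) gives 0.99992.
- At 40:40: sqrt(2/40) = 0.2236, non-centrality 5.00. The normal approximation gives 0.9988 and the non-central t 0.9986.

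The 80% is not reproduced. From these inputs it would correspond to arms of about 20:10 (79.6%) or 14:14 (81.3%), and no planned comparison is that small.

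**What would make 80% correct (non-central t).** The d detectable with 80% power is 0.547 at 80:40 and 0.634 at 40:40.

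| | 80:40 | 40:40 | Stated |
|---|---|---|---|
| Detectable difference if SD = 0.564 | 0.547 × 0.564 = 0.31 | 0.634 × 0.564 = 0.36 | 0.631 |
| The same in %, scaled by 29/0.631 | 14% | 16% | 29% |
| SD needed if difference = 0.631 | 0.631/0.547 = 1.15 | 0.631/0.634 = 0.99 | 0.564 |

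**Cross-check on the companion line.** For 11-DTX-B2, d = 24.71/43.78 = 0.564. At 80:40 this gives 82.4% (non-central t) or 83.0% (normal), close to the stated 80%. So 80:40 appears to be the intended basis. At 40:40 it would be about 70%.

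**Other readings of the CYP1A2 line.**

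- Multiplying the SD by sqrt(2), as if it needed converting to the SD of a change: 98.2% at 80:40.
- Treating 29% as a log-scale effect, ln(1/0.71) = 0.342, with 0.564 as a log-scale SD: 87.5% at 80:40 and 76.5% at 40:40.
- Treating 0.564 as a standardised effect printed as an SD: 82.3% at 80:40, with an implied SD of 0.631/0.564 = 1.12.
- Treating 0.631 as a standardised effect: 79.6% at 40:40.

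The last two come near 80%, but each assumes that a printed label is wrong, and nothing in the documents confirms either.

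**Measure.** The power line is in mL/min/kg for caffeine clearance. Protocol 3.4.2 and 7.5.2.2 and SAP 7.1.3 and 12.6.2.4 all use the unitless PX/CAF ratio, which is analysed after log transformation. An SD in mL/min/kg cannot be converted to an SD of log PX/CAF without further data. The documents give neither an SD nor an effect size for the ratio, so its power cannot be computed from them.

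**The case against.** The strongest defence is that 80% power may mean at least 80%, in which case the line is conservative on its printed inputs and not false. This does not fit the text. One sentence sets detectable differences at 80% for both markers, and the 11-DTX-B2 line does come out near 80% at the same arms. An effect twice as large in SD units cannot share that figure.

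A second defence is that nothing depends on the line. Much of this stands: Protocol 12.3 bases the sample size on the primary objective, secondary endpoints carry no multiplicity adjustment (SAP 12.1.7), and SAP section 8 omits the line. That limits the severity, but the contradiction remains.

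In the other direction, a reader might infer that the 80% is the wrong figure, that the protocol therefore understates its power, and that it should simply say above 99.9%. The documents do not support going that far. They show only that the power, difference, SD and arm sizes are incompatible. The CYP1A2 SD matches the 11-DTX-B2 standardised effect to three decimals, so a transcription or labelling slip in an input is possible; in that case 80% could be right and 99.9% would be false. This is a coincidence worth checking, not proof.

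Nor should the finding be extended to the 11-DTX-B2 line, which reproduces approximately.

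**Conclusion.** The point holds in two parts. As printed, the CYP1A2 inputs give 99.99% power at 80:40 and 99.86% at 40:40 against a stated 80%, a gap of about 20 percentage points, and which figure is wrong cannot be settled from the documents. Separately, the line powers caffeine clearance, so the planned log PX/CAF endpoint has no stated power.

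The arithmetic assumes a two-sample t comparison, the stated SD applying to both arms, and no covariate adjustment. If 0.564 is an unadjusted SD, useful baseline adjustment would raise power further, so this assumption does not explain the gap. Sample size, planned analyses and primary conclusions are unaffected. Severity is minor.

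**What to change.** 1. Check 0.631 and 0.564, including their labels and units, against the data of the earlier study from which they are said to derive.
2. Preferably replace the line with the power, or the ratio detectable with 80% power, for log-transformed PX/CAF. State the log-scale SD and its source, the day (Day 5 or Day 90) and the analysis set with its arm sizes.
3. If the clearance line is kept, correct whichever input proves wrong. Only if both inputs are confirmed, restate the power as above 99.9% at 80:40, with an 80%-detectable difference of about 0.31 mL/min/kg (14%). In either case, label the line as caffeine clearance and not the planned endpoint.

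The cost is a check of two source figures and a change of wording in the planning section. Arms, sample size and analyses stay as they are.
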